## **9 Statistical design and analysis**

The sample size for this investigation was determined based on the planned analysis for the primary objective. Sample size calculation was conducted in R using the TOSTER package. The code used to generate the sample size calculation is reproduced below.

```
TOSTER::powerTOSTpaired.raw(alpha = .05,
                           statistical_power = .8,
                           sdif = 12,
                           low_eqbound = -10,
                           high_eqbound = 10)
```

The calculation above assumes an equivalence margin of +/- 10 percentage points and a standard deviation of differences of 12. The power analysis described above yielded a sample size of 13 participants at a power of 0.8 and alpha of 0.05. An additional 3 participants will be recruited to account for potential attrition and/or missing data.

Speech intelligibility data for the primary and secondary objectives from all subjects will be analyzed. A separate analysis will be conducted for the speech intelligibility in quiet measure (primary objective) and the speech intelligibility in noise measure (secondary objective). Participants will not be grouped as a part of these analyses.

The principal investigator will conduct the analysis of the primary endpoint after data has been collected from all participants for all test conditions. This analysis will be conducted in the R statistical computing environment. The analysis will follow a two one-sample t-test procedure to test for equivalency between the aided NU6 performance in quiet and the unaided PB-max performance level. In this procedure, the two one-sample tests will compare the mean difference between the two test conditions to the equivalence margin of 10 percentage points. The two tests will differ only in their alternative hypothesis; one test have an alternative hypothesis that the mean difference is greater than the equivalence margin, the other that the mean difference is less. Rejection of both tests will be interpreted to indicate that the true mean difference is within the equivalence margin above/below zero.

The principal investigator will conduct the analysis of the secondary endpoint related to speech intelligibility in noise after all data has been collected from all participants in all test conditions. The analysis will be conducted in the R statistical computing environment. The analysis will use a paired t-test to compare the aided speech in noise performance to the unaided speech in noise performance.

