## **6 Endpoints**

Primary objective:

The NU-6 word lists are used extensively in the United States for clinical and research assessments of speech understanding and has been in use for over 50 years (Tillman, Carhart, Wilber, 1963). This test material was selected due to its long history of use in the United States as a measure of monosyllabic word recognition.

Performance on speech recognition tasks varies as a function of hearing loss (Guthrie and Mackersie, 2009). Not all patients will be able to reach 100% correct performance, regardless of the presentation level. Due to this variation, 'excellent' has been defined for this investigation as each individual participant's own maximum performance (PB-max). This investigation will aim to demonstrate equivalency on NU6 word recognition between aided performance at a typical level (65 dB(A)) and the participant's unaided PB-max.

Secondary objective:

The American English Matrix test was selected because it is an externally developed and validated speech test with a steep psychometric function. Because the test estimates an SNR-50, the steep psychometric function makes it a sensitive measure for comparing across multiple conditions. In this case, the test will be administered both with and without hearing aids. These results will be used to support the notion that hearing aids provide a clinical benefit (i.e., hearing speech in noise).

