## **10 Investigation Duration**

The expected duration for each participant is ~2-3 weeks.

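### Section 9 claims power 0.8 with 13 participants, but the planned t-tests give 0.76; 0.80 is first reached at 14, so recruiting 16 covers two losses, not three

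*Combined protocol and SAP*

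**What the plan says.** Section 9 says that the sample size was set from the planned analysis of the primary objective, and it prints the R call: "TOSTER::powerTOSTpaired.raw(alpha = .05", "statistical_power = .8", an SD of differences of 12, and bounds of -10 and 10. The prose gives the assumptions as follows: "The calculation above assumes an equivalence margin of +/- 10 percentage points and a standard deviation of differences of 12". The result is reported as "The power analysis described above yielded a sample size of 13 participants at a power of 0.8 and alpha of 0.05". The next sentence sets the allowance for losses: "An additional 3 participants will be recruited to account for potential attrition and/or missing data". That makes 16 recruited.

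The primary analysis in the same section is t-based: "The analysis will follow a two one-sample t-test procedure to test for equivalency". Equivalence is concluded only if both tests reject. Neither the prose nor the printed call states an assumed true mean difference, and the section does not say whether the calculation used a normal or a t distribution.

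Section 6 sets the comparator: each participant's own unaided maximum score (PB-max), against aided performance at 65 dB(A).

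**The concern.** A t-test on 13 paired differences estimates the SD from the data on 12 degrees of freedom. A sample-size formula that treats the SD as known is optimistic at that size, so a figure of 13 from an SD of 12 and a margin of 10 needed checking against the test that will actually be run.

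Two statements depend on the answer. One is the stated power at 13. The other is the loss allowance: adding three to 13 implies that 13 completers are enough. If they are not, the plan tolerates fewer losses than it appears to. The risk is of missing equivalence that is truly there, not of claiming it falsely.

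A related gap is that the power figure holds only for a true difference at or near zero, which the prose does not list among its assumptions. Because the comparator is each participant's own best score, a small aided shortfall is a case a reader would want to see.

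**Working it through.** **Inputs (all from Section 9, except the last).** Alpha 0.05 for each one-sided test; target power 0.80; SD of paired differences 12 points; margin ±10 points; both tests must reject. True mean difference 0 is an assumption, because the documents give none; with symmetric bounds it is the most favourable case.

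**Step 1: reproduce the plan's 13.** With the SD treated as known,

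n = (z₀.₉₅ + z₀.₉₀)² × (SD/margin)² = (1.645 + 1.282)² × (12/10)² = 12.33, rounded up to 13.

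The approximate power at 13 is 2Φ(10√13/12 − 1.645) − 1 = 2Φ(3.005 − 1.645) − 1 = 0.826, and at 12 it is 0.786. So 13 is what the normal approximation returns.

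**Step 2: power of the planned t-tests.** Both tests reject when the absolute mean difference is less than 10 − t₀.₉₅,ₙ₋₁ × s/√n. The probability of this was integrated over the chi-square distribution of s², for normally distributed differences.

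At n = 13 the critical value is t₀.₉₅,₁₂ = 1.782 and the noncentrality is 10√13/12 = 3.005. Each one-sided test alone has power 0.8818. The chance that both reject is therefore about 2 × 0.8818 − 1 = 0.764, and the full integration gives the same.

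| Completers | Losses from 16 | Normal approximation | Planned t-tests |
|---|---|---|---|
| 12 | 4 | 0.786 | 0.710 |
| 13 | 3 | 0.826 | 0.764 |
| 14 | 2 | 0.859 | 0.808 |
| 15 | 1 | 0.887 | 0.845 |
| 16 | 0 | 0.909 | 0.875 |

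Simulation with 2,000,000 draws gave 0.764 at 13, 0.808 at 14 and 0.875 at 16. The smallest number with power of at least 0.80 is 14.

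**Step 3: a non-zero true difference.** The documents give no expected shortfall, so these values are assumed (SD 12, planned t-tests).

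| Assumed aided shortfall | 13 completers | 16 completers |
|---|---|---|
| 0 points | 0.764 | 0.875 |
| 2 points | 0.69 | 0.80 |
| 3 points | 0.61 | 0.71 |
| 5 points | 0.41 | 0.48 |

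The largest shortfall that keeps power at 0.80 is about 2.0 points with 16 completers, 1.5 with 15 and 0.65 with 14. With 13 it is not reached even at zero.

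**Step 4: a different SD.** The plan gives no source for 12. At zero difference, power for 13 and 16 completers is 0.81 and 0.91 if the SD is 11.5, 0.67 and 0.80 if it is 13, and 0.57 and 0.72 if it is 14. Power of 0.80 at 13 completers needs an SD of no more than about 11.6.

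**The case against.** The strongest defence is that this is not a slip in arithmetic. The plan names its package, prints the call and reports the output, and 13 follows from the printed inputs under a recognised approximation. That is right, and it explains the figure. It does not make the stated power true of the test to be run, which is what Section 9 says the calculation was based on. That the call used the normal approximation is inferred from the match, but the power of 0.764 at 13 does not depend on that inference.

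The second defence is size. The difference is one participant, 16 are recruited, and power falls short only if all three spares (3/16 = 19%) are lost. Section 10 makes heavy loss less likely: "The expected duration for each participant is ~2-3 weeks". An SD of 11.6 instead of 12 would also close the gap. All of this stands and limits the point to a correction of stated figures.

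Third, the t-based power is exact only for normally distributed differences, whereas percent-correct scores are bounded. This is fair, and the revised text should name the assumption. Any power figure for a t-test carries it, including the one now in the plan.

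Fourth, planning at zero difference follows naturally from an equivalence aim, and the shortfalls above have no source in the documents. That is also fair. The shortfall figures illustrate sensitivity and are not a finding that a shortfall is expected; the core point stands without them.

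**Conclusion.** The concern holds. With the plan's own SD, margin and alpha, normally distributed differences and a true mean difference of zero, the planned tests have power 0.764 at 13 completers, 0.036 below the stated 0.80. Fourteen completers are needed, so 16 recruited leave room for two losses.

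The consequence is modest. The trial as recruited has power 0.875 with no losses and 0.808 with two, and the documents give no expected loss rate against which to judge three. The error is in the stated power and the implied allowance, not in the design. The unstated zero difference is a reporting gap in the same paragraph. It matters because even full completion gives less than 0.80 once the true aided deficit exceeds about 2 points. This should be corrected, and it is not a reason to change the trial.

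**What to change.** Replace the two sentences in Section 9 on the sample size and the additional participants with wording such as: 'Assuming normally distributed differences with SD 12 and a true mean difference of zero, the planned two one-sided t-tests have power 0.76 with 13 evaluable participants, 0.81 with 14 and 0.875 with 16. Sixteen participants will be recruited, which allows for two losses.'

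Add one line of power at non-zero differences, labelled as assumed, for 13 and 16 completers: 2 points 0.69 and 0.80; 3 points 0.61 and 0.71; 5 points 0.41 and 0.48. This line helps a reader interpret a result that fails to show equivalence, but the correction of the main figures does not depend on it.

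The cost is a few sentences. The recruitment target, margin and test stay as they are. The stated power at 13 becomes less favourable, the loss allowance goes from three to two, and the added line makes visible how little aided shortfall the design can absorb. If the sponsor prefers to keep an allowance of three, 14 + 3 = 17 would have to be recruited.

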## **8 Measurements and procedures**

This investigation will evaluate the clinical benefit of the Virto P hearing instruments, and it will generate data to substantiate the claim that Virto P hearing instruments provide the end user with "excellent speech understanding." Virto P hearing instruments are custom, in-the-ear (ITE) devices produced by

Sonova AG under its flagship brand, Phonak. Virto P devices are intended to compensate for mild to profound hearing loss by amplifying speech and other acoustic input to a level that is audible, yet comfortable, for the patient.

One of the most important clinical benefits of any hearing instrument is to provide improved speech intelligibility in difficult listening situations. To evaluate this benefit, participants in this investigation will complete speech-in-noise testing in both an aided and unaided condition. If Virto P is providing the intended benefit, participants should, as a group, perform better in the aided condition than in the unaided condition.

For the purposes of generating data to substantiate the claim that Virto P provides “excellent speech understanding,” ‘excellent’ has been defined as the best possible speech understanding score a user is able to achieve when asked to listen to and repeat words in quiet. This maximum level of understanding will be established for each participant in the unaided condition, and testing will be repeated at a conversational level in the aided condition. Equivalence (defined as +/- 10 %-age points) between these two measures will show that users can understand as much speech as their auditory system will permit when using Virto P and listening to speech at a typical intensity level.

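### Section 9 sets both one-sided tests for the primary equivalence analysis against the same value of 10 points, so as written they can never both reject

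*Combined protocol and SAP*

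**What the plan says.** The test is described in the primary-analysis paragraph of Section 9 (Statistical design and analysis):

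- Both one-sample tests "compare the mean difference between the two test conditions to the equivalence margin of 10 percentage points".
- On how the tests relate to each other, the plan states: "The two tests will differ only in their alternative hypothesis".
- The alternatives are: "one test have an alternative hypothesis that the mean difference is greater than the equivalence margin, the other that the mean difference is less".
- If both tests reject, the true mean difference is taken to lie inside the margin on either side of zero.

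Elsewhere the plan uses two bounds:

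- The sample-size code in Section 9 ("TOSTER::powerTOSTpaired.raw(alpha = .05" and following lines) has "low_eqbound = -10" and an upper bound of 10.
- The sentence after the code says that the calculation "assumes an equivalence margin of +/- 10 percentage points and a standard deviation of differences of 12".
- Section 8 (Measurements and procedures) has "Equivalence (defined as +/- 10 %-age points) between these two measures".

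Neither Section 6 nor Section 9 says whether the difference is aided minus PB-max or the reverse.

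**The concern.** A two one-sided tests procedure needs two reference values. One test must show that the mean difference lies above the lower bound, the other that it lies below the upper bound. Section 9 gives one value, without a sign, and places the two alternatives on opposite sides of it. A reference value of -10 appears nowhere in the description of the tests.

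This paragraph is where the plan sets out the primary test, and it conflicts with the code that sized the trial. To run the intended analysis, the analyst has to override the written text. The analysis carried out would then depart from the described procedure on the endpoint meant to support the claim of excellent speech understanding.

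**Working it through.** **Inputs (Section 9).** Alpha 0.05 for each one-sided test; target power 0.80; SD of the paired differences 12; bounds -10 and +10 in the code; stated N = 13, plus 3 for attrition, so 16 recruited.

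**1. Which test the sample size belongs to.** The normal-approximation formula for a paired equivalence test with bounds -10 and +10 and a true difference of 0 is

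n = (z(1-alpha) + z(1-beta/2))² × (SD/margin)² = (1.645 + 1.282)² × (12/10)² = 12.33, rounded up to 13.

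This reproduces the plan's 13, so the trial was sized for the two-bound test.

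**2. The tests as written.** Both use the same statistic, t = (mean difference - 10)/SE. At n = 13 (12 degrees of freedom) the one-sided 5% critical value is 1.782. Rejecting both requires t > +1.782 and t < -1.782 on the same data. That is impossible whatever the data, so the probability of concluding equivalence is 0. Simulation with 400,000 replicates per setting gave 0 at n = 13 and n = 16, for true differences of 0, +10, -10 and -20.

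**3. Worked example: n = 13, observed mean difference 0, observed SD 12.**

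SE = 12/√13 = 3.328.

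| | Test for greater | Test for less | Equivalence |
|---|---|---|---|
| As written (both against 10) | t = (0 - 10)/3.328 = -3.005, p = 0.9945 | t = -3.005, p = 0.0055 | Not shown |
| Against -10 and +10 | t = (0 + 10)/3.328 = +3.005, p = 0.0055 | t = -3.005, p = 0.0055 | Shown |

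The 90% CI half-width is 1.782 × 3.328 = 5.93, so the interval is -5.9 to +5.9, inside the bounds.

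**4. A partial repair.** Suppose the conflict were settled by keeping only the test for less than +10, with the difference taken as aided minus PB-max. At n = 13 and SD 12 that test rejects with simulated probability above 0.999 when the true aided deficit is 10 points. It gives no protection against an aided score well below PB-max.

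**5. The two-bound test.** Type I error is 0.05 at a true difference of either -10 or +10. Exact t-based power at true difference 0 and SD 12 is 0.764 at n = 13, 0.808 at n = 14 and 0.875 at n = 16.

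**The case against.** The best defence is that the intent is obvious. The margin is defined as two-sided earlier in the same section and again in Section 8, the code has both bounds, and the decision rule speaks of both sides of zero. Only one assignment of the bounds lets both tests reject: greater than -10 and less than +10. Because the literal version can never succeed, the slip would be noticed at once, and under the both-must-reject rule it could not produce a false claim of equivalence. An unsigned 10 is also a common shorthand for a symmetric margin.

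Most of this stands. The intended test is recoverable, and the zero probability describes a literal execution that an experienced analyst would not carry out. The direction of subtraction does not alter the conclusion when the bounds are symmetric; it matters for reporting the estimate and for saying which test guards against an aided deficit. The power figures are a separate matter.

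It does not make the paragraph correct. The sentence that the tests differ only in their alternative might be stretched to fit two bounds if it stood alone. Beside it, however, the plan names one comparison value and refers both alternatives to that same margin. If the margin is read as both bounds, the tests differ in reference value as well as in direction, which the text denies. The quoted code is a power calculation and does not specify the analysis.

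**Conclusion.** The concern holds. The primary hypotheses are wrong as written: a literal analysis cannot conclude equivalence, even with an observed mean difference of exactly zero. The impossibility depends on no assumption about the data. The p-values and interval in the example rest on n = 13, a mean difference of 0 and the plan's SD of 12; the power figures also assume normally distributed differences.

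The error is confined to the description of the hypotheses. The margin, alpha, both-must-reject rule and sample-size code agree with a standard two one-sided tests procedure. It should be corrected because it concerns the primary analysis, but it does not call the design into question.

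**What to change.** Replace the description of the two tests in Section 9 with:

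> Let d be the aided NU-6 score at 65 dB(A) minus the unaided PB-max score, in percentage points. Two one-sided one-sample t-tests will be done, each at alpha = 0.05: (1) H0: mean d ≤ -10 against H1: mean d > -10; (2) H0: mean d ≥ +10 against H1: mean d < +10. Equivalence is concluded only if both null hypotheses are rejected, that is, if the 90% CI for mean d lies within -10 to +10.

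Delete the sentence that the tests differ only in their alternative, and keep the rule that both must reject.

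The cost is one wording change, best made before data are seen. Data collection and the planned recruitment of 16 are unaffected. As a separate sizing point that this change neither causes nor cures, t-based power at n = 13 is 0.76, not 0.80. It passes 0.80 at n = 14, which recruitment of 16 covers if no more than 2 participants are lost.

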## **10 Investigation Duration**

The expected duration for each participant is ~2-3 weeks.

## **11 Data handling and management**

This investigation will utilize electronic CRFs, including Microsoft Excel and Word files. For all CRFs, the participants will be identified only by an anonymous code, which will not include their real names, initials, birthdates, or other identifying information. The code list will be stored separately on a restricted access server maintained by Sonova USA. All investigators and study staff will have access to CRFs during the course of the investigation. Following the completion of this investigation, CRFs will be locked and maintained in the TMF.

Any paper-based data will be stored in a locked filing cabinet at the investigation site. All electronic data will be stored on an access-restricted server owned, operated, and maintained by Sonova USA. Servers used to store data in this investigation are physically located in the US.

The identifiable data kept at PARC will be destroyed as soon as the final analyses have been completed. The de-identified data will be kept for seven years after the publication of results. When the data are destroyed, paper records will be shredded by services provided at PARC. Electronic data will be encrypted as de-identified NOAH packages, where applicable, to be shared with Sonova Switzerland.

## **12 Amendments to the CIP**

If it is necessary to make an amendment to this CIP, the changes to the CIP will be clearly identified with the date the change was made, and the version number will be incremented. Non-substantial amendments (e.g., correcting a typographical error) will be recorded as a minor version incrementation, whereas substantial amendments (e.g., a change to the study procedure or statistical plan) will be recorded as a major version incrementation. In an emergency situation, this CIP will be amended and updated only after participant health and safety have been assured and FDA/WIRB have been notified (as applicable).

## **13 Deviations from clinical investigation plan**

Deviations from the CIP to protect the rights, safety and well-being of human participants under emergency circumstances may proceed without prior approval of the sponsor and the EC – such deviations will be documented and reported to the sponsor representative (Study Manager) and the EC as soon as possible. Apart from that the investigator is not allowed to deviate from this CIP unless that deviation does not influence the investigation data.

## **14 Device accountability**

Copy from chapter 12.1(Accountability for investigational device)

The PI or authorized designee keep records documenting the following in a written process:

- Names of participants who received, used, returned, or disposed of device

- Date of receipt, identification, and quantity of each investigational device (batch/serial number or unique code)
- Expiry date (if applicable)
- Date(s) of use

The PI or authorized designee keep records documenting the following in a written process:

- Date on which the device was returned (if applicable)
- Date of return of unused, expired, or malfunctioning investigational devices (if applicable)
- Date and documentation of disposal of devices as per sponsor instructions (if applicable)

